### C.7.7 Laboratories

CBC, CMP and BNP will be performed as part of the screening phase (Visit 1) as previously outlined. CMP, BNP will be performed at visits 6, 7, and 12. All laboratories will be drawn at the Children’s Medical Center by a medical professional experienced in phlebotomy. As previously mentioned, topical anesthetic will be used when deemed appropriate. After proper labeling, blood will be sent to the Children’s Medical Center laboratory for immediate analysis. Urine pregnancy tests will be performed only on female participants 12 years of age and will be performed at Children’s Medical Center during the screening phase.

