#### **C.2.1.a Inclusion Criteria Screening Phase**

To be eligible for this trial the subjects must meet all of the following inclusion criteria at the time of enrollment:

- 1) Informed consent of parent(s) or legal guardian; informed consent or assent of subject as applicable.
- 2) Male or female children between the ages of 10 and 35 years with congenital heart disease that has been palliated with a Fontan circulation.

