#### **C.2.1.c Exclusion Criteria Screening Phase**

To be eligible for this trial, the subjects must meet none of the following exclusion criteria at the time of enrollment:

- 1) The use of beta blockers within 2 months of randomization
- 2) Patients actively listed for transplantation at time of entry into the study or anticipated to undergo heart transplantation, interventional catheterization, or corrective cardiac surgery during the 7 months following entry into the study
- 3) Sustained or symptomatic ventricular dysrhythmias uncontrolled by drug therapy or the use of an implantable defibrillator, and/or significant cardiac conduction defects, e.g., 2nd degree or 3rd degree AV block, or sick sinus syndrome, unless a functioning pacemaker is in place

- 4) Uncorrected obstructive or severe regurgitant valve disease, nondilated cardiomyopathy, or significant systemic ventricular outflow obstruction
- 5) Known renovascular hypertension or evidence of pulmonary hypertension (pulmonary vascular resistance > 6 Wood units) unresponsive to vasodilator agents such as oxygen, nitroprusside, or nitric oxide
- 6) History or current clinical evidence of moderate-to-severe fixed obstructive pulmonary disease or severe reactive airway diseases (e.g., asthma) requiring hospitalization within the past 2 years or patient currently using long-term inhaled bronchodilators
- 7) Renal, hepatic, gastrointestinal, or biliary disorder that could impair absorption, metabolism or excretion of orally administered medication
- 8) Concurrent terminal illness or other severe disease (e.g., active neoplasm) or other significant laboratory value(s) which, in the opinion of the investigator, could preclude participation or survival
- 9) Endocrine disorders such as primary aldosteronism, pheochromocytoma, hyper- or hypothyroidism, insulin-dependent diabetes mellitus
- 10) Unwillingness or inability to cooperate, or for the parents or guardians to give consent, or for the child to give assent, or any condition of sufficient severity to impair cooperation in the study
- 11) Pregnancy or possible pregnancy at time of randomization, or female of child bearing potential who are lactating, or sexually active and not taking adequate contraceptive precautions (e.g., intrauterine device or oral contraceptives for 3 months prior to entry into the study)

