#### **C.6.2.b Protection Against Risks**

To minimize the potential risks listed in Section C.6.1 the following steps will be taken:

1. The starting doses of carvedilol will be low and will be up-titrated carefully (see Table 1).
2. Subjects with known renal dysfunction will be excluded from the study.
3. Blood draws, to the extent possible, will be performed after the application of a topical anesthetic cream.
4. Serum creatinine, BNP, hemoglobin, hematocrit, AST and ALT will be measured as during the screening phase. Serum creatinine, BNP, AST and ALT will be measured during the treatment phase (Table 5).
5. Pregnancy or a planned pregnancy during the trial are exclusion criteria. A urine pregnancy test will be obtained during the screening phase. A statement regarding the potential risk of one of the study drugs will be given to female subjects of child-bearing potential and to the parents of female subjects less than 18 years of age. They will be asked questions about the subject's sexual activity. In addition, this risk is listed in the consent and the assent. Written documentation of birth control measures will be required for female subjects who are sexually active.
6. The study sponsor will pay for all testing that is not part of routine care.

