**Table 4. Screening Measures**

Screening Phase	
	Visit 0 (week -2-0)
Exercise Test	x
Pregnancy Test	x*
BNP, CBC, CMP	x

\*to be performed on females of child bearing age only (12 years of age or older)

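### C.7.7 and Table 4 give different ages for the screening pregnancy test, and even the Table 4 rule leaves girls of 10–11 with child-bearing potential without one

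*Combined protocol and SAP*

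**What the plan says.** Two places state who is tested. C.7.7 (Laboratories): "Urine pregnancy tests will be performed only on female participants 12 years of age". The Table 4 footnote, in the screening schedule: "to be performed on females of child bearing age only (12 years of age or older". A third, C.6.2.b item 5, says "A urine pregnancy test will be obtained during the screening phase" and gives no age.

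Eligibility in C.2.1.a covers "Male or female children between the ages of 10 and 35 years". Exclusion 11 in C.2.1.c begins "Pregnancy or possible pregnancy at time of randomization", with no age limit, and goes on to exclude a "or female of child bearing potential who are lactating, or sexually active and not taking adequate contraceptive precautions".

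The other safeguards are in C.6.2.b item 5. "A statement regarding the potential risk of one of the study drugs will be given to female subjects of child-bearing potential", and also to the parents of female participants under 18. Questions are asked about sexual activity. "Written documentation of birth control measures will be required for female subjects who are sexually active". None of these has a lower age limit. C.5.4 stops study drug permanently for pregnancy or planned pregnancy. B.5.4 explains the exclusion by the lack of adequate safety studies in pregnancy. Table 5 (treatment phase) has no pregnancy-test row.

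**The concern.** There are two parts, of different weight.

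First, two operative passages disagree on the age rule for a safety test. C.7.7 is the section that describes the laboratory work, and its word *only* turns an incomplete age phrase into a restriction.

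Second, once C.7.7 is brought into line with Table 4, the test rule is still narrower than the exclusion it serves. Exclusion 11 bars pregnancy at any age, while the test starts at 12 and enrolment starts at 10. A girl of 10 or 11 who has reached menarche can be enrolled and given study drug with no objective check. Every remaining safeguard for her depends on what she or her parents report, and the C.5.4 stopping rule acts only once a pregnancy is known. What is at stake is possible fetal exposure to a drug whose safety in pregnancy the protocol itself calls inadequately studied.

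**Working it through.** The plan gives no figure to reproduce, so the check is a comparison of age coverage, followed by a rough illustration of size.

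**Coverage of eligible females, ages 10 to 35 (C.2.1.a)**

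| Rule | Tested | Not tested |
|---|---|---|
| C.7.7 as printed | 12 | 10–11 and 13–35 |
| Table 4 footnote | 12–35 | 10–11 |
| C.6.2.b item 5 | age not stated | age not stated |
| Proposed rule | 12–35, plus post-menarchal 10–11 | pre-menarchal 10–11 |

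C.6.2.b item 5 conflicts with neither specific rule. It also does not override them, since both restrict the test with *only*. Aligning C.7.7 with Table 4 removes the contradiction and leaves ages 10–11. Table 5 adds no later test for them.

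**How many girls the remaining gap could involve**

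Inputs from the documents: 30 participants (C.8.2) and an estimated 50% female (C.3.1), so 30 × 0.50 = 15 females. The documents give no age distribution and do not mention menarche. The shares below are assumptions, chosen only to show a range.

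Expected number = 15 × (share aged 10–11) × (share of those who are post-menarchal)

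- Low: 5% aged 10–11, 10% post-menarchal. 15 × 0.05 × 0.10 = 0.075.
- Central: ages uniform over the 26 single years 10–35, 25% post-menarchal. 15 × 2/26 × 0.25 = 0.29.
- High: everyone aged 10–18 (nine single years), 50% post-menarchal. 15 × 2/9 × 0.50 = 1.67.

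These are expectations, not bounds. Treating the 15 females as independent, with per-female probability q equal to the product of the two shares:

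| Scenario | q | P(at least 1) | P(at least 3) |
|---|---|---|---|
| Low | 0.005 | 0.07 | 0.00005 |
| Central | 0.0192 | 0.25 | 0.003 |
| High | 0.111 | 0.83 | 0.23 |

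Zero to two extra tests is therefore the likely range, though under the high scenario three or more would occur about 23% of the time. The numbers count girls who would go untested. Missed pregnancies would be far rarer, and nothing in the documents allows an estimate of them.

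**The case against.** The strongest reply is that the conflict is editorial. Testing only 12-year-olds in a trial of ages 10 to 35 is not a plausible instruction, Table 4 states the rule in full, and C.6.2.b says a test will be obtained. A lost ≥ sign in C.7.7 is also possible, though C.8.1 retains that symbol. This largely stands: the intended reading is clear, and the first part is a wording correction.

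A reader might take C.7.7 literally and infer that most females go untested. With 15 females, ages 13–35 would make up 15 × 23/26 = 13.3 under uniform ages, or 15 × 6/9 = 10.0 if all are aged 10–18. The documents do not support that inference, because Table 4 resolves the ambiguity, so these figures carry little weight.

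The second reply is that the exclusion still operates at ages 10–11. That is correct. A reader might infer that Table 4 replaces exclusion 11 with an age rule, or that a post-menarchal girl of 10–11 is herself excluded. Neither follows. Table 4 decides only who receives a urine test, and exclusion 11 applies at every age. In that criterion, child-bearing potential qualifies the clause on lactation and contraception, not the clause on pregnancy. A girl is not excluded for having reached menarche.

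The third reply is that age 12 is a legitimate working definition of child-bearing age, that menarche is a term from outside the documents, and that the uncovered case needs an undisclosed pregnancy at 10 or 11. This stands as to rarity. It does not remove the gap, because an objective test is there to back up reporting, and for these girls there is none.

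Finally, the size range is about 22-fold (1.67 / 0.075) and rests on assumed shares. That is fair, and the range should be read as an illustration only.

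**Conclusion.** The point holds as a minor participant-safety correction. C.7.7 most likely lacks *or older* and should be made to agree with the Table 4 footnote. After that, eligible girls of 10–11 with child-bearing potential still have the pregnancy exclusion applied only through history, sexual-activity questions and contraception documentation, with no urine test at screening or later.

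The number of such girls cannot be computed from the documents. The illustrative expectation of 0.1 to 1.7 (central 0.3) depends on the assumed age and menarche shares and on the planned 15 females. It should not be read as an estimate of missed pregnancies. Randomization, the power calculation and the primary analysis are unaffected.

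**What to change.** State one rule in C.7.7 and in the Table 4 footnote, and have C.6.2.b item 5 refer to it. Suggested wording: *A urine pregnancy test will be performed at screening for every female participant who is post-menarchal or aged 12 years or older; menarche status will be recorded at screening.* If the sponsor prefers to keep the threshold at age 12, the minimum change is to add *or older* in C.7.7, which leaves ages 10–11 as they are.

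The cost is a few words in two places, a cross-reference, one extra screening question and probably zero to two additional urine tests. No change to the sample size, visit schedule or analysis is needed.

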## **C.8. Statistical Analysis Plan**

### **C.8.1. Statistical Analysis**

Each exercise outcome is a continuous variable. Linear mixed-effects models will be used to estimate the difference in the average post-phase outcomes between Carvedilol and placebo, adjusting for pre-phase values, study phase (treatment phase 1 or 2) and treatment sequence. Exploratory subgroup analyses will be performed by grouping patients according to ventricular morphology (right/mixed versus left), baseline serum B-type natriuretic peptide ( $\geq 100$ pg/ml vs.  $< 100$ pg/ml). P-values  $< 0.05$  will be considered statistically significant.

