increased systemic vascular resistance. Systemic vascular resistance is increased in Fontan patients which may adversely affect function of the single ventricle. Therefore, carvedilol may provide more physiologic benefit than other more selective beta blockers.

Potential participants in this study are patients with SV who have undergone Fontan palliation, who are now between the ages of 10 years and 35 years. Participants will initially undergo a screening phase which will include an exercise test to determine if they can adequately perform a maximal exercise test ( $\text{RER} > 1.0$  at maximal exercise) and safety laboratories. Participants who are able to exercise as described and who have acceptable safety laboratories will be randomly assigned to receive either carvedilol or placebo for the first 12 week treatment period. After a 6 week washout period, all participants will cross over to the other treatment arm for 12 weeks. Exercise data will be collected at baseline and at 12, 19, and 30 weeks after randomization. The primary aim of the study is to compare the effect of carvedilol therapy to that of placebo therapy on exercise performance as measured by peak oxygen consumption per kilogram. Secondary endpoints include the following: peak heart rate during exercise, submaximal exercise capacity, ventilatory efficiency of carbon dioxide, and safety profile of carvedilol in Fontan patients. The total sample size target of 30 participants will be recruited over approximately 24 months.

There is a lack of controlled clinical trials that have systematically investigated whether carvedilol will benefit Fontan patients. The results of this study will provide preliminary efficacy data for carvedilol in Fontan patients and inform the design and sample size calculations necessary for a large multicenter trial.

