### **C.7.3. Exercise Testing**

All Exercise Tests for study purposes will be performed at the Children's Medical Center of Dallas. Studies will be performed by experienced pediatric EKG technicians and exercise physiologists. An attending cardiologist will be immediately available per institutional protocol for any adverse event experienced during the exercise test. The exercise test will provide peak oxygen consumption, peak heart rate, ventilatory efficiency of carbon dioxide as well as submaximal exercise test performance. As previously described these data are associated with outcomes in the SV population and therefore were chosen as the primary and secondary endpoints. Exercise tests will be performed on Visit 1, 6, 7, and 12.

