### **C.8.2. Power Calculations**

All power calculations were done with consultation from a biostatistician, assuming an alpha level of 0.05 and 2-sided hypothesis testing. Average peak  $VO_2$  for Fontan patients in a large multi-institutional study was 26ml/kg/min. A previous study in adult heart failure demonstrated that a 6% increase in peak  $VO_2$  was associated with reduction in cardiovascular mortality and cardiovascular hospitalization. Therefore we conservatively chose a 10% change in peak  $VO_2$  to be clinically meaningful, setting the desired detectable difference in the change in peak  $VO_2$  to be 2.6ml/kg/min. The standard deviation of peak  $VO_2$  in the before mentioned multi-institutional study was 6.3ml/kg/min. Prior research in a different study of adults with pulmonary and cardiac disease suggests that repeated  $VO_2$  measurements are highly correlated ( $r=0.95$ ). To be conservative, for the purposes of power calculations we used an r-value of 0.8, allowing us to estimate the standard deviation of the  $VO_2$  change scores to be  $\sim 3.98$ . Under these assumptions, enrolling  $n=20$  subjects in this cross-over trial provides 80% power to detect a clinically significant difference between subjects' peak  $VO_2$  under the 2 treatment conditions' (Carvedilol vs. placebo). Therefore, a goal of 30 enrolled study participants was set to account for potential non-completion of the trial.

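### C.8.1 does not say how the two pre-phase values enter the mixed model; a single common-slope column can cost precision that the C.8.2 power figure, which has no baseline term, does not reflect

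*Combined protocol and SAP*

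**What the plan says.** C.8.1 gives the primary analysis in one sentence: linear mixed-effects models for the "difference in the average post-phase outcomes between Carvedilol and placebo, adjusting for pre-phase values, study phase (treatment phase 1 or 2) and treatment sequence". Under C.7.3, "Exercise tests will be performed on Visit 1, 6, 7, and 12", so each subject has two pre-phase tests (Visits 1 and 7) and two end-of-phase tests (Visits 6 and 12). Nothing in the document states the coding of the pre-phase values, the random effects, the covariance structure or the degrees-of-freedom method.

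C.8.2 works with a difference of 2.6 ml/kg/min, an SD of 6.3 and a two-sided alpha of 0.05. On correlation it says: "To be conservative, for the purposes of power calculations we used an r-value of 0.8". From these it derives an SD of about 3.98 and concludes that 20 "subjects in this cross-over trial provides 80% power to detect a clinically significant difference". Enrolment is set at 30 to allow for non-completion.

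**The concern.** C.8.1 and C.8.2 do not describe the same analysis. The power figure belongs to a paired difference between two end-of-phase values. The planned model adds a baseline covariate that differs between the two phases of the same subject.

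Suppose that covariate enters as one column (Visit 1 for phase 1, Visit 7 for phase 2) with one slope. The slope is then driven mainly by the strong relation between subjects: fitter patients score higher at every test. The treatment contrast, however, is made within subjects, where the relation between a change in baseline and a change in outcome may be much weaker. Applying the large slope to the difference between the Visit 1 and Visit 7 values subtracts noise from the contrast.

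At stake is the precision of the primary result with about 20 to 30 subjects. The overview also says that the results will "inform the design and sample size calculations necessary for a large multicenter trial", so the variance from this model will be carried forward.

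**Working it through.** **Inputs from C.8.2.** SD 6.3, r = 0.8, difference 2.6, n = 20, "assuming an alpha level of 0.05 and 2-sided hypothesis testing". The correlations among all four tests are not given. Every structure below is therefore an assumption, and all data are taken as complete.

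**1. The plan's own figure.** SD of the paired difference = 6.3 × √(2 × (1 − 0.8)) = 3.98, as stated. SE at n=20 = 3.98/√20 = 0.89. By the noncentral t, power is 79% (df 19, or df 18 with a period term). The stated 80% is reproduced with no baseline term.

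**2. What one column does.** Let w be the same-phase and c the cross-phase correlation. The two post-phase values differ with variance 2σ²(1 − c), and so do the two pre-phase values. The true within-subject slope is γ = (w − c)/(1 − c). If the model applies slope β to the baseline difference, the variance of the contrast is multiplied by 1 + β² − 2βγ. This exceeds 1 whenever γ is below β/2.

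- All r = 0.8: γ = 0. The fitted one-column slope averages 0.756 in REML simulation at n=20. Factor = 1 + 0.756² = 1.57, and SE = 0.89 × √1.57 ≈ 1.12. Simulation gives 1.10 to 1.13.
- Same-phase 0.88, cross-phase 0.80: γ = 0.08/0.20 = 0.40 and the fitted slope is about 0.86. Factor = 1 + 0.74 − 0.69 = 1.05, close to break-even.

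**3. Power.** Fits were post-phase value on treatment, phase, sequence and the baseline coding, with a random subject intercept, REML and a t reference. The split uses the subject's mean of the two pre-phase values plus the phase-specific deviation. Ranges show the spread over separate runs and df choices.

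| Assumed correlations | n | No baseline | One column | Split |
|---|---|---|---|---|
| All 0.80 | 20 | 79% | 60–62% | 75–77% |
| All 0.80 | 30 | 93% | 78–80% | 92% |
| All 0.85 | 20 | 89% | 71–73% | 87% |
| All 0.90 | 20 | 97% | 85–86% | 96% |
| All 0.95 | 20 | >99% | 98–99% | >99% |
| Same-phase 0.85, cross-phase 0.80 | 20 | 79% | 70–72% | 78–81% |
| Same-phase 0.88, cross-phase 0.80 | 20 | 79% | 78–80% | 83–85% |
| Same-phase 0.90, cross-phase 0.80 | 20 | 79% | 85–86% | 87–88% |
| Decay over study weeks | 20 | 79% | 70–72% | 78–80% |

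The no-baseline column for r = 0.85, 0.90 and 0.95 follows step 1 with SDs 6.3√0.3 = 3.45, 6.3√0.2 = 2.82 and 6.3√0.1 = 1.99.

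**4. Which pattern is plausible?** The overview states: "Exercise data will be collected at baseline and at 12, 19, and 30 weeks after randomization". Same-phase tests are therefore 12 and 11 weeks apart, while Visits 6 and 7, in different phases, are 7 weeks apart. Elapsed time alone does not make same-phase tests the best correlated. The decay row uses 0.95 × exp(−weeks/104.7), which is 0.95 at lag 0 and 0.80 at the 18-week gap between Visits 6 and 12. Both r values are in C.8.2; the decay form is my assumption. A phase-level factor could raise same-phase correlation, and the documents do not exclude one.

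**5. Carryover.** Take a residual of 1.0 ml/kg/min at Visit 7 in the carvedilol-first sequence (illustrative), with all r = 0.8. One column shifts the estimate by +0.756/2 = +0.38 if the residual is gone by Visit 12, and by 0.38 − 0.50 = −0.12 if it fully persists. The split, with within-subject slope near 0, gives 0.00 and −0.50.

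**The case against.** The strongest reply is that no figure in the plan is wrong. Powering on the unadjusted paired contrast and then adjusting for baseline is common, and the loss arises only under one coding that C.8.1 does not name. C.8.2 also chose r = 0.8 as a cautious value below the 0.95 it cites. In the upper part of that range one column still exceeds 80% at n=20. Twenty completers is itself a low case when 30 are enrolled. This stands, and it makes the size of the loss conditional. It does not remove the point: one phase-specific column is the ordinary way to fit the sentence, it is less efficient than the split at every uniform r tried, and at r = 0.8 it needs nearly all 30 enrolled to finish to reach the intended power.

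The split is not uniformly better. When within-subject and between-subject slopes are equal, one column is ahead by a trivial amount (99.6% against 99.4% in one such case at n=20). Its carryover behaviour is different rather than plainly superior.

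A reader might also infer a change-from-pre analysis from C.8.2, which speaks of "setting the desired detectable difference in the change in peak" VO2 and of change scores. That contrast would have SD 6.3 × √0.8 = 5.63 at uniform r = 0.8 and about 50% power at n=20. The documents do not support this reading. C.8.1 models post-phase values, C.8.2 ends by comparing peak VO2 under the two treatment conditions, and 3.98 is the SD of a single paired difference. The wording is loose; it is not a competing planned analysis.

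**Conclusion.** The point holds as a specification gap with a possible cost in precision. With r = 0.8 assumed for all four tests and complete data, the one-column model inflates the SE by about 25% and lowers power at 20 completers from 79% to about 60–62%; the split keeps about 75–77%. The loss shrinks at higher uniform r. Against no baseline term it disappears when same-phase r reaches about 0.88 with cross-phase r 0.80.

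Two stronger conclusions should not be drawn. The trial cannot be said to have 62% power, because neither the coding nor the correlations are fixed. Nor is the treatment estimate shown to be biased: without carryover, simulated means stayed within about 0.03 of 2.6 under every coding. The omission is certain; its size is not. It should be fixed before unblinding.

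**What to change.** **C.8.1.** For all exercise outcomes, enter the pre-phase value as two terms: the subject's mean of the two pre-phase values, and the phase-specific deviation from that mean. Name a random subject intercept, REML, and Kenward-Roger or Satterthwaite degrees of freedom. The df choice is secondary: simulated type I error at n=20 was 5.1–6.2% with a t reference and about 6.7–7.5% with a z reference.

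A simpler acceptable alternative is the Visit 1 value only. It is the same in both phases, so it cancels from the within-subject contrast and leaves the paired comparison unchanged (79% at n=20). It gains nothing if a within-subject relation exists.

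**C.8.2.** Say that the 80% is for the unadjusted paired difference between the two end-of-phase values, and clarify the change-score wording. Then give power for the chosen model with its assumed same-phase and cross-phase correlations.

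**Cost.** Wording only: no new visits, data or patients. The split uses one degree of freedom and gives up about 2–3 points of power at n=20 if there is no within-subject relation. Compared with one column, it is less biased by a Visit 7 residual that has gone by Visit 12 and more biased by one that fully persists. The SAP should state that trade-off.

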#### **C.2.1.d Exclusion Criteria Treatment Phase**

To proceed to randomization and treatment phase of the trial the subjects must meet none of the following criteria after the screening phase:

- 1) Hypoalbuminemia defined as serum albumin <2.0g/dL
- 2) Renal dysfunction defined as serum creatinine >2.0mg/dL
- 3) Hepatic dysfunction defined as serum AST and/or ALT > 3 times upper limit of normal (approximately 120 IU/L however, will vary depending on age),
- 4) Significant anemia or polycythemia defined as hemoglobin >18gm/dL or hemoglobin <7gm/dL
- 5) Severely elevated serum BNP defined as BNP>300pg/ml

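### The exploratory BNP analysis reduces a continuous baseline value to two groups at 100 pg/ml without a stated reason; a treatment-by-continuous-BNP term would usually estimate effect modification more precisely at no cost in data

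*Combined protocol and SAP*

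**What the plan says.** Section C.8.1 plans linear mixed-effects models for the exercise outcomes and then adds: "Exploratory subgroup analyses will be performed by grouping patients according to ventricular morphology (right/mixed versus left), baseline serum B-type natriuretic peptide". The BNP groups are at or above 100 pg/ml and below 100 pg/ml. No continuous BNP term is named, no interaction test is described, and the choice of 100 is not explained.

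BNP is available as a number before treatment. Section C.7.7 says: "CBC, CMP and BNP will be performed as part of the screening phase (Visit 1) as previously outlined". Tables 4 and 5 list it at screening and at Visit 1.

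Section C.2.1.d bars from randomisation any subject with "Severely elevated serum BNP defined as BNP>300pg/ml". The only BNP level that the documents link to outcomes is also 300 pg/ml (section B.5.1).

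The Overview says that the results should "inform the design and sample size calculations necessary for a large multicenter trial". Section C.8.2 bases its power calculation on 20 subjects and sets enrolment at 30 to allow for non-completion.

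**The concern.** Cutting a measured covariate treats a subject with very low BNP and one at 99 pg/ml as the same, and subjects at 99 and 101 as different. If the effect of carvedilol changes gradually with BNP, the two-group contrast estimates that change less precisely than a slope fitted to the measured values. This is a separate matter from whether an interaction is formally tested, because a correct interaction test on the split has the same loss.

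Entry is capped at 300 pg/ml, so the upper group can hold only values from 100 to 300. If few subjects fall there, the contrast would rest on those few. With 20 to 30 subjects there is little information to spare, and a later trial would inherit a wider interval than the data require.

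**Working it through.** **Inputs from section C.8.2.** Two-sided alpha 0.05 ("assuming an alpha level of 0.05 and 2-sided hypothesis testing"); target difference in peak VO2 "to be 2.6ml/kg/min"; the SD of peak VO2 "in the before mentioned multi-institutional study was 6.3ml/kg/min"; correlation 0.8 ("for the purposes of power calculations we used an r-value of 0.8").

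**Assumed, because the documents do not say.** The BNP distribution, the share p of subjects at or above 100 pg/ml, and the shape and size of any effect modification. Each is varied below.

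**1. The plan's own figure.** SD of the within-subject difference = 6.3 × √(2 × (1 − 0.8)) = 3.98. With n = 20 the noncentrality is 2.6 / (3.98/√20) = 2.92. Paired t power is 0.79, and the normal approximation gives 0.83. The stated 80% is reproduced.

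**2. Information kept by the cut.** This is the squared correlation between the covariate and its two-level version. For a normal covariate and linear modification it equals φ(z_p)² / (p(1 − p)).

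| Share ≥100 | Calculation | Kept | Lost | 20 subjects worth | 30 subjects worth |
|---|---|---|---|---|---|
| 50% | 0.3989² / 0.25 | 63.7% | 36.3% | 12.7 | 19.1 |
| 20% | 0.2800² / 0.16 | 49.0% | 51.0% | 9.8 | 14.7 |
| 10% | 0.1755² / 0.09 | 34.2% | 65.8% | 6.8 | 10.3 |

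**3. Other shapes.** Take BNP as lognormal, truncated at 300 and cut at 100, with assumed medians of 10 to 150 pg/ml and log-SD of 0.5 to 1.3.
- Modification linear in log BNP: the loss runs from about 33% to nearly 100%.
- Modification linear in raw BNP: from about 28% to nearly 100%.
- Example, median 50 and log-SD 1.0: 52% lost on the log scale and 30% on the raw scale. With log-SD 1.3 the raw-scale loss is 28%.
- A true step at 100 pg/ml: no loss.

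**4. Size of the upper group.** If 10% of subjects are at or above 100, the expected number is 2 of 20 or 3 of 30. The chance of none is 0.9^20 = 12% or 0.9^30 = 4%. The chance of two or fewer (binomial) is 68% or 41%.

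**5. Illustrative power.** Simulated paired differences D = slope × z + N(0, 3.98), with z standard normal (log BNP in SD units), a t test of the slope on n − 2 degrees of freedom and 40,000 replicates. Simulation error is about a point.

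| n | Slope (ml/kg/min per SD) | Continuous | Cut, 50% ≥100 | Cut, 20% | Cut, 10% |
|---|---|---|---|---|---|
| 20 | 2.6 | 74% | 51% | 39% | 26% |
| 20 | 1.3 | 27% | 18% | 15% | 11% |
| 30 | 2.6 | 90% | 71% | 57% | 40% |
| 30 | 1.3 | 39% | 26% | 21% | 15% |

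A closed-form noncentral t that uses only the step 2 efficiencies gives higher values at n = 20 and slope 2.6: 79% continuous, 60% at a 50/50 cut and 49% at 20/80. It holds the covariate at its expected spread and does not count the gradient left inside each group as extra residual variance. The ordering is the same.

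The simulation uses 3.98 as the SD around the slope. Section C.8.2 gives it as the SD of change scores overall. With a slope of 2.6, the total SD implied here is √(3.98² + 2.6²) = 4.75.

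**The case against.** The analysis is labelled exploratory, a prespecified cut is not an error, and the stored BNP values can be analysed continuously later. All of that is true, and it limits the importance of the point.

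The large power contrasts need a very large gradient. A slope of 2.6 per SD is the trial's whole target effect for each SD of log BNP, so subjects at +1 and −1 SD would differ by 5.2 ml/kg/min, or 20% of the mean of 26. Nothing in the documents supports that. At 1.3 per SD neither analysis is well powered, and the change would seldom alter a conclusion. This stands.

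The log scale is not always better. If modification is linear in raw BNP (truncated lognormal, log-SD 1.3), the log slope keeps 69% against 71% for the split at a median of 30, and 74% against 72% at a median of 50. In most other scenarios examined the log term did better. This is why a raw-scale check belongs in the fix.

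A reader might infer that the plan certainly discards at least a third of the BNP information, or most of the gradient. The documents support neither. A loss of at least a third requires a normal covariate and linear modification. A loss of most of the gradient requires an unequal split of about 20/80 or worse, since a 50/50 split keeps 64%. A reader might also infer that the upper group will be tiny. The cap at 300 makes that possible, but the share at or above 100 is not given.

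**Conclusion.** The point holds as a low-priority improvement. The plan uses a continuous, already collected covariate only as two groups, at a value that it does not justify, in a trial sized on 20 subjects with 30 enrolled. Under a roughly normal log BNP and linear modification the loss is 36% at best and about half to two thirds if 20% or 10% of subjects are at or above 100 pg/ml. It can be about 28-30% if modification is linear in raw BNP, and nil if there is a true step at 100, for which the documents offer no evidence.

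The practical gain is a tighter estimate of the gradient and less dependence on how many subjects happen to fall above the cut. It should not be presented as a reliable gain in significant findings. The Overview speaks of preliminary efficacy data and of design and sample-size input for a later trial. It does not say that this trial is meant to identify who benefits, so the point should not be argued on that ground. The primary analysis, the sample size and the safety comparison are unaffected.

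**What to change.** In C.8.1, define the exploratory BNP analysis as a treatment-by-log(baseline BNP) term, with the log BNP main effect, in the mixed model already planned. State that the BNP value is the one taken before the first treatment period and, because Tables 4 and 5 both list a draw, which visit it comes from. Report the slope with a 95% confidence interval and the estimated carvedilol-placebo difference at the 25th, 50th and 75th percentiles of BNP. Repeat with raw BNP as a sensitivity check. Keep the split at 100 pg/ml for descriptive display, with the number of subjects in each group.

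The cost is a sentence or two of text and no new data, visits or procedures. The small downside is that the term assumes a roughly linear shape, which 20 to 30 subjects can check only roughly.
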